12.1.2 Surgery Visit (Visit 00 and Visit 00A)

Visit 00: Day 0 (implant for Eye 1)

Visit 00A: 7-14 days after surgery for Eye 1 (implant for Eye 2)

Below is a list of study procedures to be undertaken at surgery visit. Procedures should be performed in the order presented below. Activities involving multiple delegated staff members may be performed in parallel. All assessments must be recorded in source documentation and eCRFs (if applicable).

Procedures to be performed in the CRS eye:

1. Document any changes to ocular and nonocular concomitant medications.
2. Prepare subject /operative eye for surgery in accordance with site specific operating procedures.
3. Create a 4.8 to 5.5 mm anterior capsulotomy centered on the line of sight using the LenSx femtosecond laser.
4. Remove the cataract by phacoemulsification using Centurion.
5. Record use of CDE.
6. Record estimated aspiration fluid.
7. Record phacoemulsification aspiration time.
8. Record aphakic refraction and aphakic spherical equivalent (SE).
9. Record IOL power recommended by VerifEye+ (or Lynk) and predicted post-op SE.

10. Record implanted IOL power and predicted post-op SE.
11. Record surgical problems, complications, or other events that occur during surgery.
12. Record any device deficiencies and AEs. Refer to Section 13 for further detail.

Procedures to be performed in the Standard Manual Technique eye:

1. Ensure IOL power calculation was performed.
2. Document any changes to ocular and nonocular concomitant medications.
3. Prepare subject /operative eye for surgery in accordance with site specific operating procedures.
4. Create a 4.8 to 5.5 mm anterior capsulotomy centered on the line of sight using the manual technique.
5. Remove the cataract by phacoemulsification using the Centurion.
6. Record use of CDE.
7. Record estimated aspiration fluid.
8. Record phacoemulsification aspiration time.
9. Perform manual limbal relaxing incision (LRI). Manual LRI will only be performed on astigmatism of > 0.50 D, including any known surgically induced astigmatism, according to the Verion measurements obtained at Screening.
10. Record implanted IOL power and predicted post-op SE.
11. Record surgical problems, complications, or other events that occur during surgery.
12. Record any device deficiencies and AEs. Refer to Section 13 for further detail.

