Section 6	
Revised text from:
 
Verion (Measurement Module and Vision Planner) IOL calculation will only be used on the test eyes.
	To clarify that only the vision planner portion is to be used and that it will be used on both eyes

	To Verion Vision Planner IOL calculation will only be used on both eyes.	
Section 12	Added LenStar Perform Keratometry with LenStar	To clarify that the LenStar will be used for keratometry
Section 12	Added below text: Assess for irregular corneal astigmatism by evaluating the relevant irregularity index and the appearance of the topography maps. Document on the printed maps whether or not there is significant irregular corneal astigmatism and provide a justification for the assessment.	To elaborate on the corneal topography assessment that will be used for the relevant exclusion criterion

5.2 Amendment 1

Purpose of Amendment: To implement revisions based on the change in IOL platform from monofocal to multifocal (ReSTOR +2.5 IOL)

[figure not shown]
Rationale: To align with business/reimbursement strategy

Current Study Status: Planning

Case Report Form Revision Required:	 Yes	 No
Informed Consent Modifications Required:	 Yes	 No
Applicable Investigators:	 All	 Selected (list below)

Itemized Changes:

Objectives (Protocol Section 1 and Section 8)

Eligibility Criteria (Protocol Section 1 and Section 10)

Criterion	Rationale
Added an inclusion criterion, “target is emmetropia (+0.50 to -0.50)	To ensure no monovision treatments are planned
Changed minimum age from 21 to 22	To be consistent with age defined as adult for other trials executed in US
Replaced monofocal IOL implantation with ReSTOR +2.5 D IOL	To align with business/reimbursement strategy

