7 INTRODUCTION

7.1 Background

Cataract is the leading cause of blindness in the world, and cataract surgery is one of the most commonly performed operations in the Western world. Preferred surgical techniques have changed dramatically over the past half century with associated improvements in outcomes and safety. Femtosecond laser platforms that can accurately and reproducibly perform key steps in cataract surgery, including corneal incisions, capsulotomy and lens fragmentation, are now available (Day 2016). According to the World Health Organization (WHO), an estimated 20 million people worldwide are blind due to bilateral cataracts (Baltussen 2004).

Over the past decades, the safety and effectiveness of cataract surgery has improved, but cataract patients continue to have high expectations when it comes to their postoperative refractive outcomes. Modern cataract surgery is becoming a refractive procedure, and surgeons not only aim to remove the cataractous lens successfully but also to reduce or eliminate pre-existing refractive errors. Published literature reports 71% and 47% of post cataract removal patients are within ± 0.5 D and ± 0.25 D respectively of the biometry prediction error. It is interesting to note that only two thirds of the study population planned for emmetropia became emmetropic (Behndig 2012). Although there are reports on preoperative biometry prediction and astigmatism management (Behndig 2012, Hatch 2015), it is necessary to address the role of other variables such as posterior corneal curvature to total astigmatism and standard intraocular lens (IOL) calculation.

Although there are published results regarding the individual devices of the Cataract Refractive Suite (CRS) (Hatch 2015, Nemeth 2015, Woodcock 2016, and Ianchulev 2014) and retrospective study of the use of the major components of the CRS (AnalyzeOR Retrospective Data Exploration Study, data on file), there is no prospective study that reports the refractive outcomes produced by using the major components of the CRS together.

The aim of this study is to assess the refractive accuracy when using the combined CRS for surgical planning and lens removal and to compare these results with those obtained using the standard manual technique.

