11 TREATMENT

Throughout the clinical study, the Investigator will be responsible for ensuring that the clinical study products are not used in any unauthorized manner.

Table 11-1**Treatments**

	Test article: CRS	Control articles: Standard manual technique
Administration	Intervention during preoperative planning and during cataract surgery	Intervention during surgery
Manufacturer	Alcon Laboratories, Ft. Worth, TX, USA	--

11.1 **Investigational Products**

Test Article: CRS composed of the following:

1. Verion Image Guided System which comprises of the following:
 - Verion measurement module
 - Verion visionplanner
 - Verion digital marker
2. LenSx femtosecond laser
3. ORA with VerifEye+ (with or without the VerifEye Lynk)

The CRS is a collection of advanced technologies that is designed to guide informed surgical decisions, minimize potential sources of error, and may allow surgeons to be more consistent in delivering the desired refractive outcomes. The main focus in cataract surgery is toward achieving better refractive outcomes, and the CRS helps to achieve this goal because each component enhances accuracy in the many steps of the surgical procedure. The CRS may improve refractive outcomes by integrating the different technologies that are used from the planning stage to surgery to postoperative follow-up. It gives the surgeon the capability to access, review and analyze their postoperative data all in one location and personalize surgeon factors to further optimize their results.

The Verion Image Guided system performs 3 functions: diagnostic imaging, surgical planning, and surgical guidance. The Verion Reference Unit is comprised of the Verion measurement module and the vision planner. The measurement module obtains a digital image of the eye and performs keratometry and pupillometry measurements. The Verion vision planner—performs IOL power selection and astigmatism management—uses the data from the measurement module. The reference image and the surgical plan are then exported to the Verion digital marker L and digital marker M that creates a computer-generated tracking overlay for the LenSx laser and the surgical microscope respectively. The image and overlay support eye tracking and registration while providing a real-time guide for accurate capsulotomy creation, corneal incisions, and IOL positioning.

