Control Articles: Standard manual technique and manual limbal relaxing incisions as necessary. If a manual limbal relaxing incision is needed, the calculation will be based on the output of the Verion measurement module and Vision planner taken at Screening. The control procedure is standard biometry for IOL calculation and cataract removal using phacoemulsification technique.

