11.2 Usage

Verion reference unit and Verion digital marker:

Plausibility of measurement: Ensure the cornea is in natural condition before performing a Verion measurement. Normal conditions might be violated after direct cornea contact. Do not perform more than 15 measurements per session per eye.

The user should check all measurement readings for plausibility. Ensure that the subject is not wearing contact lenses during the time of reference measurement. Dry eyes might impact the accuracy and robustness of the keratometry measurement. It may not be possible to carry out measurements on subjects with fixation problems. Reference measurements results for subjects with a non-intact cornea (eg, due to cornea implants, corneal transplants, corneal scarring, keratorefractive surgery, or irregular cornea) or pathologies that influence the appearance of limbus, pupil and/or iris may be incorrect. In such cases, a cross-check with other alternative diagnostic devices/methods is mandatory. Always check status for plausibility. Reference measurements on such subjects may be incorrect. Measurements of pseudophakic subjects may be incorrect or not possible due to the reflexes of the IOL.

The user should check all measurement readings for plausibility. This involves verifying the registration proposals of the Verion digital marker between reference and microscope image, as well as verifying limbus detection during live tracking. An irregular elliptic limbus may not be detected correctly during the surgery.

Refer to the user manuals for the Verion reference unit and the Verion digital marker for a complete description of proper use and maintenance of these devices, as well as a complete list of contraindications, warnings and precautions.

Refer to the LenSx laser operator's manual for a complete listing of indications, warnings and precautions.

Refer to the ORA VerifEye+ operator's manual for a complete description of proper use and maintenance of these devices, as well as a complete list of warnings and precautions.

The control procedure (standard manual technique) is standard biometry for IOL calculation and cataract removal using phacoemulsification technique.

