9. Perform corneal topography. Assess for irregular corneal astigmatism by evaluating the relevant irregularity index and the appearance of the topography maps. Document on the printed maps whether or not there is significant irregular corneal astigmatism and provide a justification for the assessment.
10. Perform Keratometry measurement with LenStar
11. Use the Verion Vision Planner for IOL power calculation.(refer to MOP for details).
12. Perform biometry (LenStar) (refer to MOP for details).
13. Identify target refraction.
14. Perform intraocular pressure measurement. IOP should be measured only after all biometric and topographic measurements are performed (refer to MOP for details).
15. Conduct dilated fundus examination (refer to MOP for details).
16. Record any device deficiency and AEs.
17. Randomize the subject.

NOTE: Randomization must be completed following all Screening procedures and confirmation of subject eligibility prior to surgery (this includes TBUT*).

*If subject starts warm compresses after the screening visit, the subject must return prior to surgery day (Visit 00: Day 0) to have TBUT reassessed. If the TBUT is < 10 secs in either eye, the subject must be discontinued from the study as a screen fail. If the TBUT is \geq 10 secs in each eye, the subject may be randomized and continue in the study. The warm compresses regimen must be maintained for the duration of the study. Record TBUT in source.

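### Is the predicted refraction that scores the primary endpoint left without a defined source?

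*Protocol*

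**What the plan says.** **Endpoint.** Protocol 8.4.1 and 15.4.1.1 and SAP 5.1 and 5.2.1 score an eye by whether its Month 1 spherical equivalent (SE) lies within 0.50 D of the predicted value. The visible text names no device, formula or time point for the prediction.

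**Recording.** Protocol 12.1.2, step 10, has the same instruction for the CRS eye and the control eye: "Record implanted IOL power and predicted post-op SE". In the CRS eye, step 9 also records the lens power that VerifEye+ recommends, with a predicted SE for it. Table 6-1 marks predicted SE at Visit 0 and not at the surgery visits. Section 12.1.1 shows no step that records it.

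**Control-eye lens calculation.** Section 11.1 says: "The control procedure is standard biometry for IOL calculation and cataract removal using phacoemulsification technique". Section 11.2 repeats it: "The control procedure (standard manual technique) is standard biometry for IOL calculation and cataract removal using phacoemulsification technique". Table 11-1 describes the test article alone as "Intervention during preoperative planning and during cataract surgery", and the list of test-article components includes "Verion visionplanner". Table 6-1 footnote f reads "Verion Vision Planner IOL calculation will only be used on both eyes". Step 11 of 12.1.1, under a visit covering both eyes, reads "Use the Verion Vision Planner for IOL power calculation".

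**The concern.** The prediction is half of the primary outcome, so its source determines what the McNemar test compares. The stated aim in 7.1 is to "assess the refractive accuracy when using the combined CRS for surgical planning and lens removal", which takes in preoperative planning. If the Vision Planner supplies the control prediction, both arms share a test-article component and lens planning differs only by the intraoperative ORA step. If a separate calculation supplies it, planning is part of the contrast. Sites reading different sections could mix the two within the control arm.

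In CRS eyes, Verion calculates first and ORA then confirms or revises (9.4.2). Two predictions could therefore exist for one lens, and step 10 names neither. A reference left open until data are in hand also invites a choice made after seeing results.

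**Working it through.** **1. The plan's own figure.** Inputs from protocol 15.10: rates 83% and 75% (d = 0.08), discordance ψ = 0.21 or 0.33, one-sided 5%, power 90%, Miettinen approximation:

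n = [1.645ψ + 1.282·√(ψ² − d²(3 + ψ)/4)]² / (ψd²)

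- ψ = 0.21: n = 266.4, so 267, as stated.
- ψ = 0.33: n = 432.05, so 433, as stated.

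**2. How much rescoring would matter.** With 267 pairs:

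- Pairs in which only the CRS eye succeeds: 267 × (0.21 + 0.08)/2 = 38.7, about 39.
- Pairs in which only the control eye succeeds: 267 × (0.21 − 0.08)/2 = 17.4, about 17.
- z = (39 − 17)/√(39 + 17) = 22/√56 = 2.94, against a critical value of 1.645.

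Suppose k CRS eyes were rescored from success to failure:

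- All from pairs where both eyes succeed: z = (22 − k)/√(56 + k), which is 1.75 at k = 8 and 1.61 at k = 9.
- All from pairs where only the CRS eye succeeds: z = (22 − k)/√(56 − k), which is 1.77 at k = 10 and 1.64 at k = 11.

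The threshold is crossed at a net 9 to 11 eyes, or 3.4% to 4.1% of 267. This margin would apply to any scoring question in this trial, and it moves eyes in one direction only. The documents give no size or sign for a difference between candidate predictions, so it does not measure this gap.

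**3. The candidate predictions side by side.**

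| Candidate | Arms | Lens it refers to | Where it appears |
|---|---|---|---|
| Screening value | Both | Lens planned before surgery (inferred from timing) | Table 6-1 mark; no visible step in 12.1.1 |
| Step 9 value | CRS only | Lens recommended by VerifEye+ | 12.1.2 |
| Step 10 value | Both | Implanted lens | 12.1.2 |

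The endpoint compares the achieved refraction with what was predicted. The achieved refraction belongs to the implanted lens, so the prediction must too. Step 9 has no control-arm counterpart. The screening value predates any ORA revision. Only step 10 exists in both arms and refers to the implanted lens.

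**4. CRS eyes.** Section 11.1 and Table 6-1 footnote i put the ORA-recommended power in the test eye. When that power is implanted, steps 9 and 10 concern the same lens, and step 9 ties its prediction to VerifEye+. When another power is implanted, step 10 still holds the value for the lens in the eye. No text directs step 10 back to the Verion prediction.

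**5. Control eyes.** The operating text (footnote f and 12.1.1 step 11) applies the Vision Planner without restriction to one arm. The Section 11 phrase can be read as naming the measurements and the planner as the calculator. Steps 10 to 12 of 12.1.1 place LenStar keratometry, the planner and LenStar biometry together, and LenStar is the only biometry device that Table 6-1 schedules. Section 11.1 itself bases any control-eye limbal relaxing incision on Verion output, so it does not confine Verion to test eyes. The link from LenStar to the planner is an inference, but it makes the passages compatible.

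**The case for a change.** The strongest contrary case is that the visible text does not name the reference, and that reading the passages as compatible takes some charity. The control-article paragraph in 11.1 names Verion for the relaxing incision and then uses a different phrase for lens calculation, as if the two differed. Section 12.1.1 asks for its steps in the listed order, yet the planner comes before LenStar biometry. Control step 1 in 12.1.2 asks only that a calculation was performed. The SAP (effective 06-Mar-2017) predates protocol Version 3.0 (04-Apr-2017) and does not resolve the matter.

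Much of this stands as description. The visible endpoint definitions lack a one-line derivation. Table 6-1 has no surgery-visit marks in the row for predicted SE. The wording of Section 11 does not match that of Table 6-1 and 12.1.1, and which description of control-eye planning holds is for the sponsor to state when the two are reconciled.

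It does not follow that the analysis would go wrong. Whichever calculation a control eye had, step 10 records the prediction for the lens it received, so its prediction error remains well defined. The open question is how to describe the control arm, not how to score an eye. The SAP's date adds little, because no visible itemised change in either protocol amendment alters the endpoint definition. The choice left open at analysis is narrow, because one recorded value fits both arms. Mixing of methods across sites is possible but not shown: sites work from Section 12 and the manual of procedures, and step 11 refers to that manual.

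**Conclusion.** The concern does not call for a change to the plan. The missing derivation is a gap that analysts fill sensibly: they take Month 1 SE at Visit 3A minus the step 10 predicted SE, with success at an absolute difference of 0.50 D or less, in both arms. The data are already collected. The missing Table 6-1 marks and the unaligned wording in Section 11 are clerical, and no stated rule has been shown to give a wrong result.

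The effect on the primary result cannot be sized from the documents. The margin of 9 to 11 eyes describes the design's general sensitivity and is no estimate of harm from this gap.

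The conclusion rests on two assumptions: that step 10 in CRS eyes carries the prediction accompanying the implanted lens, and that the Section 11 phrase describes inputs to the planner. It also rests on incomplete text. The manual of procedures was not supplied, SAP 2.1 is empty in the available text, and parts of SAP Section 5 are not shown. Any of these may already define the reference, so the finding is only that the visible text does not.

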12.1.3 Visit 1 (Day 1 for Eye 1)

1. Document any changes to ocular and nonocular concomitant medications.
2. [REDACTED]
3. Perform slit-lamp examination.

4. Perform IOP measurement.
5. Record any device deficiencies and AEs. Refer to Section 13 for further detail.

12.1.4 Post-Surgery Visit (Visit 1A, 2A, 3A and Visit 4A)

Below is a list of study procedures to be undertaken at post-surgery visits. Procedures should be performed in the order presented below. All assessments must be recorded in source documents and eCRFs (if applicable).

Ocular assessments are to be performed in the study eye only.

1. Document changes in ocular and nonocular concomitant medications at Visit 1A, 2A, 3A, and Visit 4A.
2. [REDACTED]
3. [REDACTED]
4. [REDACTED]
5. [REDACTED]
6. Perform manifest refraction assessment at Visit 1A, 2A, 3A, and Visit 4A. However, at Visit 1A, assessments will be performed at the Week 1 visit for eye 1 only (Refer to MOP for details).
7. [REDACTED]
8. Perform slit-lamp examination at Visit 1A, 2A, 3A, and Visit 4A. Refer to MOP for details.
9. [REDACTED]
10. [REDACTED]
11. Perform Keratometric measurements at Visit 3A and Visit 4A.
12. Perform IOP at Visit 1A and 4A only. IOP should be measured after all VAs, corneal

measurements and refractive findings have been obtained. Refer to MOP for details.

13. Perform dilated fundus exam at Visit 4A only. Refer to MOP for details.

14. Record any device deficiencies and AEs. Refer to Section 13 for further detail.

15. Document subject exit from study at Visit 4A.

12.2 Unscheduled Visits

An unscheduled study visit (USV) is defined as one that meets all of the following:

- Examination that is not standard of care and not required by the protocol.
- Examination conducted by the study staff.
- New finding, continuation of an existing finding, or a change to a previous finding is noted.

An USV may or may not result in the capture of an AE. Likewise, an AE may be captured without the report of an USV (eg, AE identified subsequent to study eye examination by non-study personnel).

The assessments captured at the USV are dictated by the Investigator per his/her medical judgment. The following assessments/documentations are recommended.

- Concomitant medications
- IOP
- [REDACTED]
- [REDACTED]
- Manifest refraction
- Slit-lamp examination
- Dilated fundus examination, as necessary
- Device deficiencies
- AEs

NOTE: Assessments/documentation are not limited to the above list.

For safety purposes, if an USV is required after the final study visit, the visit should be documented. Refer to Section 13.6 for further detail.

12.3 Missed Visit

If a subject misses a scheduled visit, reschedule the subject within the same visit period.

Diligence should be shown in trying to schedule the subject for all visits, and all attempts to contact the subject documented in the subject's chart. In documentation, include dates, times, method of contact, etc. If attempts to contact the subject are unsuccessful, the date the subject is considered lost to follow-up should be documented.

If a subject is unable to return for the final study visit, complete the Exit case report form with the appropriate reason for discontinuation indicating the subject is lost to follow-up.

